1.1 Overview of the FAITH-DM Trial

The Feeding America Intervention Trial for Health—Diabetes Mellitus (FAITH-DM) is a randomized, controlled study of the implementation of a diabetes intervention in food pantry settings. Every effort has been made to enhance the feasibility of implementation while maintaining the rigor of a randomized, controlled trial. The intervention will be implemented in three food banks: Alameda County Community Food Bank (Oakland, CA), Gleaners Community Food Bank of Southeastern Michigan (Detroit, MI), and the Houston Food Bank, (Houston, TX). These food banks were chosen through a competitive application process after demonstrating their capacity to reach the population of interest (English- and Spanish-speaking adults with diabetes receiving food at food pantries) and carry out the study procedures according to the instructions laid out in this manual.

This research is critically important. In the pilot study recently completed, we observed significant improvements in self-management skills and competencies such as self-efficacy and medication adherence, and a trend toward improved glycemic control (HbA1c) and decreased risk of severe hypoglycemic events. Participants were highly satisfied with the diabetes-appropriate food distributed as part of the intervention. This work suggested that food pantries are a feasible site to engage vulnerable individuals in diabetes self-management efforts. We are excited to be able to determine the efficacy of this model.

Funding for FAITH-DM was provided by Feeding America and the Laura and John Arnold Foundation.

The study is listed on www.clinicaltrials.gov with identifier: NCT02569060.

FAITH-DM received approval from the Western Institutional Review Board (Protocol Number: FADiabetes2015, WIRB#: 2015169).

1.2 Overview of the Manual of Operations (MOP)

A MOP is a handbook that details a study's conduct and operations. It transforms the study protocol into a guideline that describes a study's organization, operational data definitions, recruitment, screening, enrollment, randomization, follow-up procedures, data collection methods, data flow, and quality control procedures. The MOP is intended to serve as a study "cookbook" that facilitates adherence to study procedures. It is a reference guide for how each element of the study should be carried out.

Implementing a trial is a complex undertaking. The MOP is a dynamic document that will be updated throughout the study to reflect any refinements to the study protocol, forms, or procedures. It should be easily accessible, in electronic and/or printed form, at all study sites. Each page of the MOP contains the version number and date in order to allow easy tracking of revisions. As pages are

revised, an updated version number and associated date will replace the original page(s) in the MOP. All previous versions should be archived.

1.3 MOP Contents and Organization

[figure not shown]
This MOP includes the following information:

- a) Study Protocol
- b) Study Organization and Responsibilities
- c) Study Timeline
- d) Study Intervention Overview
- e) Recruitment and Participant Retention Plan
- f) Study Flow
- g) Screening and Eligibility Criteria and Processes
- h) Informed Consent and HIPAA
- i) Study Intervention
- j) Study Measurements and Procedures
- k) Safety Reporting
- l) Study Compliance
- m) Data Collection and Study Forms
- n) Data Management
- o) Quality Control Procedures
- p) Reports
- q) Data Safety and Monitoring Board
- r) Study Completion and Closeout Procedures
- s) Study Policies
- t) Appendices: contain additional information and sample forms

[figure not shown]
2 Study Protocol

For adults with diabetes mellitus, diabetes self-management education (DSME) is critical to achieving long-term control of blood sugar levels (glycemic control) and preventing diabetes-associated complications. This education is often difficult to access for highly vulnerable and marginalized adults in the United States. Furthermore, we know that the appropriate foods for a diabetic diet are often out of reach for food insecure households. The purpose of this study is to determine the extent to which food banks and food pantries can help reach this population with effective DSME, food, and access to primary health care, with the ultimate goal of reducing diabetes complications and mortality. The randomized, controlled trial design will allow us to definitively answer this question. Our primary outcome of interest is HbA1c improvement in the intervention group compared to a wait-listed control group of food pantry clients living with uncontrolled type 2 diabetes.

2.4 Coordinating Center

Coordinating center responsibilities will be shared between FANO and UCSF's Center for Vulnerable Populations. These responsibilities include:

- Development and maintenance of the MOP (UCSF and FANO)
- Development of the randomization scheme and procedures (UCSF)
- Development of the data flow and data management procedures including data entry, error identification and correction (UCSF and FANO)
- Adverse event monitoring and reporting to Coordinating Center (FANO)
- Adverse event reporting to UCSF Committee on Human Research and/or Western Institutional Review Board, and/or the Urban Institute IRB as appropriate (UCSF)
- Central communication with study sites, scheduling of meetings and training sessions, responding to and documenting ad hoc communications (FANO)
- Site visits to ensure adherence to the protocol and procedures (FANO)
- Quality control procedures (UCSF)
- Reports (e.g. enrollment, adverse events, participant status, site performance, quality control) (UCSF and FANO)
- Distribution of all changes, reports, procedures and documents to participating study sites (FANO)
- CITI Certification (FANO and UCSF, as necessary)

2.5 Study Sites

Sites participating in FAITH-DM include: Alameda County Community Food Bank (ACCFB), Gleaners Community Food Bank of Southeastern Michigan (GCFB), and the Houston Food Bank (HFB)

The roles and responsibilities of the food banks include:

- Maintenance of study binder with updated MOP
- Participation in protocol finalization and preparation of study materials
- Compliance with protocol, MOP, IRBs (UCSF Committee on Human Research, Western IRB, Urban Institute IRB) and Federal and state regulations
- Accountability for administration of study intervention
- CITI certification (as necessary)

- Membership in Steering Committee
- Recruitment, screening, enrollment, and follow-up/retention of participants
- Protection of participants' rights
- Data collection from enrollment through study completion, including: survey data, HbA1c, and health care utilization data (requiring medical chart abstraction)
- Transfer of data to Coordinating Center and resolution of all queries
- Communication of questions, concerns, and/or observations to the Coordinating Center (FANO, [name])
- Development and maintenance of MOUs with collaborating health care sites
- Communication with primary care providers
- Development of expertise in administration of all intervention components, including diabetes education
- Maintenance and quality control of point-of-care HbA1c machines and glucometers, including CLIA Certification and other regulatory requirements (as necessary)
- Assembly and distribution of food packages
- Communication and reporting per project guidelines and timeframes with FANO and UCSF staff (e.g., progress reports, budget reports, food box content reports, etc.)

2.6 Steering Committees

The Steering Committee is composed of representatives from FANO, UCSF, and staff from each of the three food banks, including the FAITH-DM Manager and the Research Assistant(s). It is responsible for the overall direction of the study.

The following areas fall under the purview of the Steering Committee:

- Review of overall design and implementation of the study
- Conduct of the study
- Approval of essential study documents, including the protocol, protocol amendments, MOP, and data collection forms
- Review of data collection practices and procedures
- Monitoring recruitment and retention of study participants
- Changes in study procedures as appropriate
- Allocation of resources based on priorities of competing study demands
- Review of study progress in achieving goals and taking necessary steps to ensuring the likelihood of achieving those goals

It is FANO and UCSF's responsibility to make sure the Steering Committee has the necessary data to make decisions related to these responsibilities.

2.7 Timeline

Timeline

	IRB Finalization, Kick-Off call, distribution of MOP	Hire Research Assistants, Kickoff Meeting	Food Bank Planning, Training	Screening & Enrollment	INT - Food Boxes & Written educational materials distributed	Educational Classes Offered as needed per site	Participant nudges for Control group & intervention group	3-month HbA1c tests	INT Follow-up surveys and HbA1c testing – T6	Control Group Surveys and HbA1c testing – T6	Control Group receives food boxes	Control group final survey and HbA1c testing – T12	Intervention group follow-up HbA1c and survey – T12; HCUS (extension activities)	Target #'s participants recruited this month per food bank	Total Numbers Recruited per food bank	Total Intervention Group at end of the month (Estimate) per food bank	# of participants receiving diabetes food boxes (assuming full participation of control group)	
July 2015	X	X	X															
August	X	X	X															
September			X															
October			X	X	X	X	X							10	10	5	5	
October Notes				Classes ideally offered twice this month														
November				X	X	X	X							20	30	15	15	
December				X	X	X	X	X						25	55	28	28	
January 2016				X	X	X	X	X						25	80	40	40	
February				X	X	X	X	X						25	105	53	53	
March				X	X	X	X	X						20	125	63	63	
April			X	X	X	X	X	X	X	X	X			30	155	73	78	
April Notes			First intervention group concludes; Team Retreat in Houston (4/20-4/21/16); begin sending and retrieving HCU surveys to all PPT providers															
May				X	X	X	X	X	X	X	X			30	185	78	93	
June				X	X	X	X	X	X	X	X			30	215	81	109	
July				X	X	X	X	X	X	X	X			25	240	81	121	
August				X	X	X	X	X	X	X	X	X		20	260	78	131	
August Notes				Screening & enrollment concludes (or earlier if goal #'s are achieved)														
September					X	X	X	X	X	X	X	X	X			66	129	

October					X	X	X	X	X	X	X	X	X			54	127
November					X	X	X	X	X	X	X	X	X			44	122
December					X	X	X	X	X	X	X	X	X			29	109
January 2017					X	X	X	X	X	X	X	X	X			14	94
February					X		X	X	X	X	X	X	X			14	77
February Notes		Final Food Boxes and Group Classes (Intervention Group); send final HCU surveys to both INT & CONT PPTs' Providers															
March							X	X	X	X	X	X	X				67
April							X	X			X	X	X				52
May							X	X			X	X	X				37
June							X				X	X	X				22
July							X				X	X	X				10
August											X	X	X				10
August Notes		Final Food Boxes Distributed (Control Group)															
September												X	X				
October													X				
October Notes		Research Assistants finish all data collection & uploads; final PCP HCUS surveys (INT only at T12); final transmissions to UCSF; final site grant reports DUE															
November		Data analysis by UCSF and Urban Institute; manuscript preparation (UCSF, UI, & FANO)															
December																	
December Notes		FAITH-DM concludes															

2.8 Communications Plan

The communication plan includes:

Steering Committee

- Monthly meetings by phone
- Ad hoc phone meetings between monthly meetings as necessary
- Email communication as necessary

FANO Staff ([name]), FAITH-DM Managers, and Research Assistants:

- Weekly meetings by phone during implementation, with frequency reduced to twice or once monthly after follow-up period is completed
- Email communication as necessary
- Quarterly brief written progress reports (including project information: food box contents, DSME activities, clinic referrals, etc.)
- Annual project and budget reporting (exact dates and forms TBD)

All changes to the study protocol will be clearly documented by email communication and revision of the MOP.

3 Study Intervention

There are four components of the intervention. Each is described below.

1. Testing and monitoring of blood glucose levels
2. Primary care coordination
3. Diabetes-appropriate food packages
4. Diabetes self-management education (DSME) and support (SMS)

3.1 Testing and monitoring of blood glucose

Sites will follow all local, county, state, and federal regulations to develop and operate a testing, screening, and monitoring program that meets compliance requirements. For specific regulatory guidelines, refer to **section 7.5**.

3.1.1 Testing for diabetes and diabetes control among food pantry clients

In order to identify food bank clients who may be eligible for study participation, food bank project staff will offer free diabetes screening events at food pantry sites during the recruitment phase of the study. Diabetes screening will be provided at no cost for any food pantry client who is interested in and verbally consents to the screening, and is over 18 years of age. Food bank staff will conduct all screening activities, emphasizing with food pantry clients that screening tests are **not** diagnostic and that clients should speak directly with their health care providers for diabetes risk assessment, evaluation, and treatment.

For food pantry clients with no reported history of diabetes, or no known history of diabetes, diabetes screening will first include a random blood glucose (RBG) test using a Point-of-Care (POC) glucometer and a finger stick capillary whole blood sample. Clients who have an elevated RBG screening result (defined as ≥ 160 mg/dL in non-fasting individuals and ≥ 140 mg/dL in fasting individuals) will also receive a screening glycosylated hemoglobin A1C (HbA1c) test using a POC device.

All screening tests will be performed by trained study or food bank staff, or by trained food bank volunteers. All study staff and volunteers with human subjects contact must have appropriate CITI certification and quality and safety training. Screening staff will complete the information on the Screening Log (Appendix B) for **every** food pantry client who receives a blood glucose and/or HbA1c test. If uncertain, staff can ask the client for specific information in order mark the appropriate boxes under “age”, “gender”, and “race/ethnicity” (otherwise, staff can complete that information based on their assessment of the client.

For food pantry clients who self-report a history of diabetes, screening will consist of a POC HbA1c test using a finger stick capillary whole blood sample performed by trained personnel.

All clients who participate in screening will receive written results of their screening tests (see Client Screening Results Form in **Appendix J**), along with basic information about their results and local community health care resources.

Additionally, any food pantry client who receives an HbA1c test will receive an educational handout (see **Appendix AK**) with information about the category in which their result falls:

- HbA1c result less than 5.7%: normal HbA1c range
- HbA1c result 5.7% to 6.4%: pre-diabetes range
- HbA1c result 6.5% to 7.4%: diabetes, controlled
- HbA1c result equal to or greater than 7.5%: diabetes, poorly controlled

Food pantry clients who have screening HbA1c test results $\geq 7.5\%$ will then be further assessed by study staff for eligibility and, if appropriate, enrollment into the study.

3.1.2 Testing random blood glucose levels

We will test food pantry clients' current glycemic status using a point-of-care (POC) glucometer that measures random blood glucose (RBG). We have chosen a glucometer that is inexpensive, reliable, and FDA-approved for use on multiple people. Specific instructions for using the GE100 Blood Glucose Monitor can be found in **section 7.2**.

3.1.3 Testing Glycosylated Hemoglobin (HbA1c) Levels

We will measure HbA1c levels for food pantry clients who report a diabetes history or who have a screening RBG result ≥ 160 mg/dL non-fasting or ≥ 140 mg/dL fasting. We will use a point-of-care (POC) HbA1C device using a small sample (1 large drop, 5 microliters [μ L]) of capillary whole blood. Instructions for using the PTS Diagnostics HbA1c+NOW[®]™ system can be found in **section 7.3**.

3.1.4 Monitoring blood glucose control among study participants

Our primary outcome of interest is change in HbA1c over time for study participants. Hemoglobin A1c testing provides a reliable estimate of general blood glucose control over an approximate three-month time frame. We include regularly scheduled HbA1c testing for all study participants throughout the course of the study following the timeframes outlined below. All HbA1c testing will be conducted by trained food bank staff or volunteers, who will use the same POC HbA1c devices described above (and in specific detail in **section 7.3**). We will conduct monitoring tests with study participants at the food pantries where participants will be going to receive food bank services. Study staff can use the “Participant Follow-Up Testing Results” form (**Appendix AU**) to record all follow-up and monitoring participant test results. All test results will be entered into the MS Access database; the database has fields for recording test results performed outside of the windows identified below.

	Intervention Group	Control Group
T0 (baseline)	At enrollment	At enrollment
T3 (month 3)	2 – 4 months (3 \pm 1)	N/A
T6 (month 6)	5 – 7 months (6 \pm 1)	5 – 7 months (6 \pm 1)
T9 (month 9)	N/A	8 – 10 months (9 \pm 1)
T12 (month 12)	11 – 13 months (12 \pm 1)**	11 – 13 months (12 \pm 1)**

* 1 month = 30 DAYS ALWAYS

** Alternatively, T12 HbA1c windows can be manually calculated as 5-7 months **after** the completion date of a participant’s T6 follow-up activities. This revision will accommodate participants who complete their T6 activities at month 5 (earliest part of the window) and maintain a 5-7 month separation between the T6 and T12 follow-up activities.

Study staff can complete “extra” HbA1c testing for study participants outside of their intervention windows (e.g., between T0 and T6 for CONT group, or between T6 and T12 for INT group) **if** a participant requests a test during a pantry visit. Staff should not complete more than 1 extra HbA1c test for a participant during their waiting period. Staff should not promote extra HbA1c testing for study participants—the primary purpose for completing extra testing during these periods is to provide a positive experience for study participants. Extra HbA1c test results should be entered in the Access database in one of the “extra test” fields.

If a participant does not complete their follow-up HbA1c test at T6 or T12, study staff can still complete an HbA1c test with the participant when they are next seen at a pantry or study activity.

Any HbA1c test completed beyond the follow-up windows should be entered in the MS Access database as an “extra” test.

3.2 Primary care coordination

MOUs with clinics require clinic staff to actively reach out to food bank-referred clients and schedule a new patient appointment within 3 months. Food bank staff / RA will need to be able to verify with the clinic that the attempt was made and that the client has an appointment for care.

A sample MOU document is included in **Appendix O**.

Based on lessons learned from the Feeding America / BMSF Diabetes Pilot Project, it is recommended that food banks complete the following activities in order to build and sustain effective food bank – clinic partnerships:

- Identify clinic point person (“clinic champion”) who will be the main contact for FAITH-DM staff
- Meet with clinic staff to brief providers on the FAITH-DM trial, health care utilization analysis, food bank resources, and food insecurity screening; attend weekly “huddles” or monthly staff meetings to inform, update, and remind clinic staff about the project and partnership

Participating clinic providers will receive a packet from FAITH-DM with:

- Background info on FAITH-DM RCT
- Overview of referral process and communication strategy for FB participants referred to clinic for care (fax process, appointment verification, etc.)
 - Clinic patients cannot be directly referred into FAITH-DM RCT
- Overview of study health care utilization plan (consent to share protected health information [PHI], HIPAA, data requests)
- Institutional Review Board (IRB) certification: Western IRB protocol # 20151569
- Contact info / signatures of UCSF MD, FANO, and participating food bank
- General information on how to:
 - Conduct food insecurity screening with patients (**Appendix P**)
 - Refer food insecure clinic patients into local hunger safety net

3.2.1 Referrals to a primary care provider (PCP)

- If food pantry client is not (and will not be) enrolled in FAITH-DM, provide resource hand out
 - For clients who report no PCP, complete “Screening and Referral Form” and fax form to appropriate provider
- If participant is enrolled in FAITH-DM, study staff will ask: “Is there a doctor, other health care provider, or clinic you usually go to in order to help you manage your diabetes?”
- Intervention participants who answer “yes” (has PCP)
 - Retrieve PCP information
- Intervention participants who answer “no” (does not have PCP)
 - Provide written information to participant on PCP resources

- Send active referral to PCP (FAX to PCP and/or phone call to PCP/clinic) using the appropriate HCUA provider letter (see **section 7.7**).
- Control participants who answer “yes” (has PCP)
 - Retrieve PCP information
- Control participants who answer “no” (does not have PCP)
 - Provide resource handout
- All study participants will again be asked at T6 and at T12 if they have a PCP; for **both** intervention group and control group participants who report no PCP at T6 or T12, provide:
 - Written information to participant on local PCP resources
 - Active referral to PCP (FAX to PCP and/or phone call to PCP/clinic) using the appropriate HCUA provider letter (see **section 7.7**).

See **Appendix AI** for the “Screening and Referral Form” to use when sending a food pantry client’s screening results to a clinic. The client must sign this form, giving food bank staff permission to share screening results with the clinic and/or provider.

Food banks must also maintain a HIPAA compliant fax to send/receive client information to/from health care partners in order to maintain security and protect client/patient medical information. To meet HIPAA standards, food banks should ensure that a dedicated FAITH-DM fax is located in a secure area (away from public areas). Staff should use the HIPAA-compliant fax cover sheet (**Appendix AB**) whenever faxing forms and information connected with the FAITH-DM study. Additionally, site staff should follow best practices to maintain protection of participant data:

- Only authorized personnel are to have access to the fax machine and incoming faxes
- Destination numbers should be verified before transmission
- Verified numbers used frequently should be pre-programmed to reduce number entry errors
- Recipients should be notified that they have been sent a fax
- Any patient data should be in the fax body and not in any of the data fields
- Faxes are to be sent to secure destinations; i.e., the fax machine of the recipient must be in a secure location, accessible only by those authorized to receive the information
- Maintain records of fax transmissions in the MS Access database for study participants

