5.2 Eligibility and Exclusion Criteria

Study eligibility is determined by a set of specific inclusion and exclusion criteria. Individuals must meet all eligibility criteria. This section defines the criteria, method for determination, and the specific forms needed to document eligibility.

Our specific inclusion criteria include:

- Type II diabetes mellitus with HbA1c $\geq 7.5\%$ using food bank point-of-care testing
- Food pantry client (defined as any individual engaging with a food bank or partner agency for food assistance, regardless if is their first visit or not, or if they are requesting direct food assistance, SNAP enrollment assistance, or general information on any food resources or programming)
- Reliable mode of contact (either phone or address) where they can be reached
- English or Spanish verbal fluency
- 18 years of age or older
- Intent to remain in the study area for at least the next 12 months
- Willingness to participate in intervention (including picking up bi-monthly food boxes and participating in diabetes education activities)

Exclusion criteria include:

- Type 1 diabetes
- Pregnant or less than 6 weeks post-partum*
- Cognitively impaired: dementia, mental illness, or active substance abuse severe enough to make client incapable of providing informed consent and could interfere with administration of the survey or participation in the intervention**
- Household member already enrolled in the study***

* Study participants who become pregnant after enrollment may remain in the study and participate in all study activities in their assigned group (intervention or control). Study staff will emphasize with any pregnant study participant the importance of staying connected with their healthcare providers (to receive regular pre-natal care and any pregnancy-specific diabetes self-management education and support).

** Refer to **Appendix AS** “Cognitive Impairment Assessment Tool” to assess cognitive impairment during participant enrollment; this form and process need only be used on clients where study staff suspect cognitive impairment.

*** Other household members with diabetes can share the food box, participate in the education, and have their HbA1c checked, but should not be enrolled in the study.

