7.7.2 HCUA Activities at Baseline (T0)

The following sections outline HCUA activities that take place when a new participant enrolls in the study.

At enrollment, all participants will be asked to provide the name of their current primary care provider (individual provider and/or practice/clinic site) and to provide consent for communication with provider, including release of medical record information (see **section 5.3** for discussion of consent and HIPAA procedures, and **Appendix AO** for the Medical Records Release Template). The site personnel will request as much contact information for the provider as possible (phone number, address, or nearest cross streets the participant can identify). The RA may need to research and complete the provider contact information if the participant is unable to provide full contact information at the time of enrollment.

If the participant declines to provide consent for the release of medical records from the current provider, this should be documented and entered into the MS Access database. No further action to request information from the provider can be taken regarding release of medical record information. However, when a participant provides informed consent to enroll in the study, study staff does receive participant permission to contact the participant's care provider to inform provider of the participant's entry into the study.

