Appendix AI – FAITH-DM Screening and Referral Form

Feeding America Intervention Trial For Health
Diabetes Mellitus

Screening and Referral Form

Date: _____ Client Name: _____
Date of Birth: _____ Client Phone: _____

A. Health Screening

Blood Glucose: _____ mg/dL Fasting Random

HbA1c: _____ % (Finger-stick sample A1CNow+ System)

Client-Reported Health History:

- Pre-DM GDM T1DM T2DM
 No known history of diabetes

Has healthcare source or PCP? Yes No

Clinic / Practice Name: _____

PCP Name: _____

Food Bank

Referring Staff Name: _____

Referring Staff Phone: _____

NOTES:

B. Referral

Referral from Food Bank to clinic / provider:

Other (e.g., Emergency Room referral):

Preferred Language

English Spanish Other:

Client Consent to Release Information:

I give my consent to the (NAME) Food Bank to share information about my screening results and the other information on this form with my doctor or a health care center.

Doy mi consentimiento para el (NAME) Food Bank para compartir información sobre los resultados de mis pruebas y el otro información en esta forma con mi médico o un centro de salud.

Client Signature / Firma

Date / Fecha

Food Bank

FAITH-DM Manager:

Street, City, State, Zip

T: ###-###-####; Fax: ###-###-####

Email:

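### Section 3.2.1 sets primary care status with a diabetes-specific question, section 7.7.2 uses a general one, and no rule says which governs, so a participant with a regular doctor can be routed two ways

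*Combined protocol and SAP*

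**What the plan says.** Section 3.2.1 scripts the baseline question for enrolled participants: "Is there a doctor, other health care provider, or clinic you usually go to in order to help you manage your diabetes". A yes is recorded as having a PCP, a no as not having one. After a no, an intervention participant gets written information and an active referral by fax or telephone. A control gets a resource handout.

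The population is wider than people with a diagnosis. Section 3.1.1 sets out a screening route "For food pantry clients with no reported history of diabetes, or no known history of diabetes": glucose first, then HbA1c if glucose is raised. Those at 7.5% or above "will then be further assessed by study staff for eligibility and, if appropriate, enrollment into the study". Section 5.2 defines the criterion as type 2 diabetes with HbA1c of at least 7.5% "using food bank point-of-care testing" and does not ask for a prior diagnosis.

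Elsewhere provider status is general. Under section 7.7.2, "all participants will be asked to provide the name of their current primary care provider". Section 13.5.1 uses the same term, and Appendix AM has a PCP name field with a no-PCP box.

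At T6 and T12, section 3.2.1 asks both arms again, in general terms, whether they have a PCP. The T6 provider survey looks back 12 months (section 7.7), so it covers the six months before enrollment.

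**The concern.** Having a doctor who helps with diabetes and having a primary care provider are different things, yet 3.2.1 treats them as one. Someone who has just learned of a high HbA1c can truthfully say that nobody helps manage their diabetes while having a regular doctor. Sections 7.7.2.2 and 7.7.2.4 send staff back to 3.2.1 for participants without a provider, so the general wording in 7.7.2 does not settle which answer counts.

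The answer decides the referral, the T0 letter and, through section 13.5.1, who receives the T6 survey. Its consequences differ by arm. Change in primary care use is the primary utilization indicator (section 13.5.2), drawn from self-report and, where available, provider reports. Pre-enrollment records lost unequally between arms would distort the provider-reported part of that comparison.

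**Working it through.** The plan states no figure on this point. The check sets the sections side by side and then gives a scale on assumed inputs.

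**Routing of one person: a regular doctor, no known diabetes**

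| Step | Coded no (3.2.1) | Doctor named (7.7.2) |
|---|---|---|
| Intervention, T0 | Active referral and Letter 2 to a partner clinic (7.7.2.2) | Letter 1, with screening results, to the regular doctor (7.7.2.1) |
| Control, T0 | Handout; Letter 3 only if primary care was received in the last six months (7.7.2.4) | Letter 3 to the regular doctor (7.7.2.3) |
| T6 survey | Whichever provider is named at T6 (7.7.3.2) | Doctor named at enrollment, plus any new one (13.5.1, 7.7.3.4) |

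The rule in 7.7.2.4 that traces a provider seen in the last six months, and stores the contact for T6, is written for controls only. Section 7.7.2.2 has no counterpart.

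**Scale**

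- Planned size: 720 (section 13.4.1), in two equal arms: 720 / 2 = 360 per arm.
- u, share enrolled with no known diabetes: not in the documents; assumed 2% to 20%.
- h, share of those with a regular doctor: not in the documents; assumed 50% to 80%. Section 13.5.3 reports that most people screened in the pilot said they had a provider, which fits at least half.
- t, share who name that doctor at T6: not in the documents; taken as 0, 50% and 90%.

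Coded no at T0, if all of them answer no and 3.2.1 alone decides: 360 × u × h.

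- Low: 360 × 0.02 × 0.5 = 3.6
- High: 360 × 0.20 × 0.8 = 57.6

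Still missed after T6: 360 × u × h × (1 − t).

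| t | Low | High | Share of arm |
|---|---|---|---|
| 0 | 3.6 | 57.6 | 1.0% to 16.0% |
| 50% | 1.8 | 28.8 | 0.5% to 8.0% |
| 90% | 0.4 | 5.8 | 0.1% to 1.6% |

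In the control arm the rule in 7.7.2.4 would recover some of these.

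**Direction**

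Section 13.5.4 estimates β3 = (post − pre, intervention) − (post − pre, control). Suppose a referred intervention participant names only the partner clinic at T6. That clinic holds later visits but none from before enrollment. The intervention pre-period count falls and β3 rises, in the direction of the hypothesis in 13.5.2. If a share s of the analyzed arm loses a mean of m pre-enrollment visits, and later visits are all captured, β3 rises by s × m, less any matching loss in controls. The documents give no visit rates, so m cannot be filled in. Any later visits to the unnamed regular doctor would also be missed, which works the other way.

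**The case against.** The case against is substantial.

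- A reader might infer that undiagnosed participants must answer no. The documents do not support that. They have just been given a result that section 3.1.1 classes as poorly controlled diabetes, and may well name their usual doctor.
- The 3.2.1 question is not the only source of status. If staff act on the name given under 7.7.2, the regular doctor is written to. Section 10.2 also speaks of the primary care provider in general terms for high results, without separating arms.
- A reader might infer that a control coded no never has a letter sent. Section 7.7.2.4 provides one when primary care was received in the last six months.
- A reader might cite Appendix AI, which asks "Has healthcare source or PCP", as a conflicting baseline record. Under 3.2.1 that form is for clients who are not enrolled, so Appendix AM is the right comparison.
- T6 gives a second chance: a general question in both arms, a survey to any provider first named then, requests to several providers where more than one is identified, and a 12-month look-back.
- The diabetes-specific wording may be deliberate, since section 13.5.2 describes provider engagement as part of diabetes management. The participant surveys are not reproduced, so their wording cannot be judged.

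All of this limits the consequences. It does not remove the contradiction: two sections define the same status differently, neither takes precedence, and the recent-provider rule covers one arm only. The T6 recovery is partial, because a referred participant may name only the new clinic.

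**Conclusion.** The inconsistency is real and the consequence minor. A participant with a regular doctor can be coded both with and without a provider at baseline, and the resulting actions differ by arm. Records are lost only if that doctor goes unnamed at both T0 and T6. An upward bias in the provider-reported estimate of primary care use is then possible. It is not established, because it also requires that later care be captured at the new clinic.

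The number affected is unknown. The ranges above rest wholly on assumed u, h and t: from under 1 to a few dozen per arm still missed where some name the doctor at T6, and up to 58 only if none do. Setting the baseline counts against the 80% and 70% provider-data goals in section 13.5.3 would be misleading, because it treats every miscoded participant as lost. Self-reported utilization is collected from all participants whatever their coding, and the HbA1c outcome and its sample size are not affected.

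**What to change.** 1. Use one general provider question, consistent with 7.7.2, in both arms to set PCP status, the T0 letter and the T6 survey recipient.
2. Record whether a provider helps with diabetes care as a separate item.
3. Apply the recent-provider rule of 7.7.2.4 to both arms when requesting records.
4. Reconcile 3.2.1 and 7.7.2 on which answer triggers the active referral. Referral is a component of the intervention, so that choice is left to the sponsor.

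The cost is one reworded question and one added item, with no extra visits or staff. Extending the recent-provider rule adds some record requests in the intervention arm.
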